## **9.2 General Guidelines for Administration of Self-report Measures**

By definition, the self-report measures will be completed by the Study Participants. Each participant will be provided access to a quiet, private, and comfortable setting in which the self-report measures can be completed. Instructions, which are included on each instrument, will be reviewed with the Study Participant to ensure that the instructions are understood. Upon completion, the Study Audiologist will verify that all pages of each instrument have been completed. The questionnaires will be administered in paper format per their standardization. The sequence for administration of these measures is described in Table 1.

#### **9.3.1.1 Tinnitus Questionnaire**

The primary outcome measure selected for the TRTT is the Tinnitus Questionnaire (TQ). The TQ, which is popular in Europe, is a broad-spectrum assessment tool with a total of 52 items. It features a 3-point response scale and can be completed easily in 20 minutes. The instrument has been widely used for clinical and research purposes and is respected for its robust psychometric characteristics (Goebel and Hiller, 1999; Nobel, 1998, 2000). Validated German and Spanish translations of the TQ are available, as is a test manual (Hallam, 1996). The instrument's five-

factor structure has been replicated in several studies attesting to its validity and generalizability. Quartile analyses have been completed for total and for all five factors, or sub-scales. The factors include:

- Psychological distress;
- Intrusiveness;
- Hearing difficulties;
- Sleep disturbances; and
- Somatic complaints

Several aspects of the TQ contribute to its appropriateness to serve as the primary outcome measure for the TRTT. The scope of the instrument and its five-factor structure are well suited to the target areas addressed in TRT and in the standard of care (SC) treatment that will be evaluated in the TRTT. Other instruments include some but not all of these focal areas. The TQ also provides a comprehensive assessment of sleep disturbances experienced secondary to tinnitus, perhaps the most vexing tinnitus problem for many sufferers (Hallam, 1996a). Sleep deprivation impacts psychological well-being, physical health, and daily functioning. Thus, evidence that treatment can improve the quality and amount of sleep for individuals who have tinnitus would have significant public health implications beyond the amelioration of tinnitus *per se*. The TQ's specificity and sensitivity make it an excellent choice for identifying treatment effects and exploring mechanisms of change.

The baseline administration of the TQ will be used to determine eligibility (score  $\geq 40$ ) for the TRTT and to provide a baseline value for comparison at follow-up. The TQ will also be administered at the 3, 6, 12 and 18 month Follow-up Visits, and annually thereafter until study close-out. The primary outcome is a repeated measures analysis of the difference between TQ score at Baseline and Follow-up visits. The difference in TQ score between Baseline and the 18 month Follow-up visit is an additional primary outcome measure. TQ factor (sub-scale) scores at the various follow-up time points will be used as secondary outcome measures.

### **9.3.1.2 Tinnitus Functional Index**

Instruments selected as secondary outcome measures for the TRTT include the Tinnitus Functional Index and the Tinnitus Handicap Inventory. The Tinnitus Functional Index is a newly developed instrument by a group of experienced tinnitus investigators and funded by the Tinnitus Research Consortium. It has 25 items and an eight-factor structure including:

- Intrusiveness;
- Reduced sense of control;
- Cognitive interference;
- Sleep disturbance;
- Auditory difficulties (related to tinnitus);
- Relaxation interference;
- Reduced quality of life; and
- Emotional distress.

Each question on the instrument has a 10-point response scale (ranging from no effect to extreme effect). The Tinnitus Functional Index, particularly designed to assess change, will be especially valuable as an outcome measure for the TRTT. It will be administered at Baseline in the TRTT and at the 3, 6, 12 and 18 month Follow-up Visits, and annually thereafter until study close-out.

### **9.3.1.3 Tinnitus Handicap Inventory**

The Tinnitus Handicap Inventory was developed by Newman *et al.* (1996). It consists of 25 items and is purported to have three factors:

- Functional;
- Emotional; and
- Catastrophic.

The 3-point response scale for the Tinnitus Handicap Inventory consists of “No, Sometimes, and Yes.” The Tinnitus Handicap Inventory has been widely used in the U.S., including by the University of Maryland Tinnitus and Hyperacusis Center (Berry, *et al.*, 2002), but significant questions have been raised regarding item selection, interpretation, and reliability, as well as the validity of the quartile analysis (Goebel and Hiller, 1999; Baguley *et al.*, 2001). In addition, Zachariae *et al.* (2000) report that a factor analysis of a Danish version of the Tinnitus Handicap Inventory did not confirm the structure reported initially. Consequently, only a total score will be used as an outcome measure.

We will use the Tinnitus Handicap Inventory as a secondary outcome measure in the TRTT to permit comparison to other outcome studies in which it has been used. It will be administered at the Randomization Visit and at the 3, 6, 12 and 18 month Follow-up Visits, and annually thereafter until study close-out.

### **9.3.2 Psychological Measures**

The psychological measures included in the TRTT represent a set of variables that are often associated with adjustment to tinnitus and other chronic health conditions. Tinnitus can be a depressing and anxiety-provoking condition. An individual’s general affect, whether positive or negative, influences the ways in which he or she copes with stress. Dispositional optimism is also related to effective management of stress. These measures will be completed by the Study Participants at the Randomization visit and at specific Follow-up Visits, as indicated in Table 1.

#### **9.3.2.1 Beck Depression Inventory Fast Screen**

The Beck Depression Inventory (Beck, Brown, and Steer, 1996) is the most widely used measure of depressive symptoms. The original inventory had 21 items, employed a 4-point Likert scale of 0-3 for each response item, and could be completed in approximately 10 minutes. The areas of assessment relate to cognitive, affective, and somatic symptoms. The Beck Depression Inventory has been used in scores of outcome studies examining treatment effectiveness with both clinical and non-clinical populations. A more recent version, the Beck Depression Inventory II, was revised specifically to conform with two-week criterion for symptom duration described in the Diagnostic and Statistical Manual, 4th Edition (DSM-IV). In addition, a 7 item version, the Beck Depression Inventory Fast Screen (or Quick Screen) was introduced with comparable psychometrics to the original version ( Benedict, *et al.*, 2003). We will use the Beck Depression Inventory Fast Screen in the TRTT.

The Beck Depression Inventory Fast Screen will be completed during the Baseline Eligibility Visit to determine whether the individual should be further evaluated for depression. The threshold score on the Beck Depression Inventory Fast Screen for determining the need for

further evaluation is a score  $\geq 4$  or endorsement (a response of 2 or 3) on item # 7 (suicidal thoughts or wishes). The Clinical Center Director must take appropriate steps with respect to requesting or scheduling an appropriate consultation for individual failing the screen. Following professional evaluation, individuals who have not passed the screen may be evaluated for eligibility for participation in the TRTT. Repeated measures of the Beck Depression Inventory Fast Screen over the course of the TRTT will permit Study Participants to be monitored for onset of serious depression as a possible consequence of treatment or other contributing factors. The TRTT will define the same threshold - a score of 4 or greater on the Beck Depression Inventory Fast Screen or endorsement of item # 7 (suicidal thoughts or wishes) - as an adverse event. The Clinical Center Director is responsible for referring the Study Participant to an appropriate health care provider in this circumstance.

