Estimates of tinnitus incidence or prevalence among military personnel from other nations vary considerably and depend on which population was studied. For example, a Finnish study reported an incidence of about 25% in 418 conscripts who suffered acoustic trauma from hand-held firearms and large caliber weapons or explosions (Ylikoski and Ylikoski, 1994). These incident cases suffered prolonged tinnitus up to a year following the noise exposure, and about 8% continued to suffer distressing tinnitus over their lifetime. Among Finnish officers, 32% (220 of 669) experienced tinnitus and 17% (118 of 669) suffered distressing tinnitus continuously. Salmivalli (1967) reported that 16% of military personnel with normal hearing sensitivity and 56.0% of those with severe hearing loss suffered from tinnitus. Similar estimates have also been reported for Israeli soldiers (Roth *et al.*, 1989). The important point is that it is reasonable to expect that a substantial proportion of the roughly 1 million active U.S. military personnel will be exposed to conditions that make them more susceptible to tinnitus than the civilian population.

Because we expect the prevalence of tinnitus is likely higher among U.S. military personnel than among the civilian population, the adverse consequences of tinnitus should reasonably be greater in the military. Significant correlations have been reported in the military population between tinnitus and depression and between tinnitus and sleep disturbances. These disturbances are appreciably higher than among normal controls (Alster *et al.*, 1993).

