#### **4.4.5 Mental Health Exclusion Criteria**

Because tinnitus may affect an individual psychologically or emotionally, Study Audiologists should carefully consider whether an individual with a recent or active mental health condition will be able to participate fully in the TRTT or complete all follow-up visits. The need to care for an individual's mental health should take precedence over participation in the TRTT.

An individual will be ineligible to participate in the TRTT if he or she:

- Is unable to participate fully in the trial or complete all followup visits because of an active or ongoing mental health condition, as assessed by best clinical judgment;
- Is feigning tinnitus or hearing loss, as assessed by best clinical judgment.

The above conditions are not intended to be an exhaustive list of exclusion criteria, nor would it be possible to compose a complete list. Each investigator is expected to use good judgement in selecting Study Participants with tinnitus that is not currently treatable by medical or surgical means, is willing to undergo the assigned study treatment regimen, and is likely available for long-term followup. The time and expense that this may require are considerable, but if Study Participants drop out of the trial, serious bias may occur in the study results. Therefore, it is imperative that every investigator screen potential Study Participants very carefully and eliminate those individuals with a poor prognosis for a good follow-up over the course of the TRTT.

---

---

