#### **5.2.3.3 Beck Depression Inventory Fast Screen**

The potential Study Participant will be asked to complete the Beck Depression Inventory Fast Screen (BB), which is a measure of depressive symptoms and consists of 7 items. Since tinnitus may be associated with depression, the Beck Depression Inventory-Fast Screen will be used to identify potential Study Participants who have depression. The TRTT will define clinical depression as a score of 4 or greater on the Beck Depression Inventory-Fast Screen or endorsement of item # 7 (suicidal thoughts or wishes). Any potential Study Participant who fulfills these criteria should be referred for appropriate counseling and may not be eligible for the TRTT.

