## **10.3 Follow-up Visits**

Follow-up Visits will take place at 3, 6, 12, and 18 months after T1, and then annually until study close-out. Study Participants in all groups are seen at all Follow-up Visits. All Follow-up Visits involve reinforcement counseling as needed.

The Clinical Coordinator or the blinded Study Audiologists (i.e., the Clinical Center Study Audiologist who is not involved in counseling the Study Participant) will complete the Follow-up Medical History Form at each follow-up visit, and ask each participant to complete the following data collection instruments: the Tinnitus Questionnaire, Tinnitus Handicap Inventory, Tinnitus Functional Index, and the Beck Depression Inventory Fast Screen at each Follow-up Visit.

The Follow-up TRT Interview and a full audiological/tinnitus/hyperacusis evaluation, consisting of audiometric pure tone, speech recognition threshold, tinnitus pitch and loudness match, loudness discomfort level (LDL), and word recognition testing will be completed at the 6, 12 and 18 months visit. In addition, the following forms will also be completed at the 6 and 18 month study visits: the Digit Symbol Substitution Test, Hearing Handicap Inventory, State Trait Anxiety Inventory, Positive and Negative Affect Schedule Life Events Checklist, and EuroQOL. It is important that the Study Audiologist who is **not counseling the Study Participant** perform these activities to preserve blinding when measuring these outcomes (see Table 10.2 ).

Note that LDL is checked at all follow up visits. At T2 and the 3 month follow-up visit (F1), the LDL is recorded on the LDL Assessment for Treatment Form for each participant, and at the 6, 12, and 18 months visits, it is recorded on the Audiological/Tinnitus/Hyperacusis (ATH) Examination. LDL testing at these visits is completed by the blinded study Audiologist who is not involved in the treatment of the Study Participant, but the counseling Audiologist may use the LDL results for treatment.

All follow-up visits past 18 months follow-up include only the tinnitus specific health-related quality of life instruments are collected (i.e, the Tinnitus Questionnaire, Tinnitus Functional Index, and Tinnitus Handicap Inventory). These forms may either be completed in person or mailed and returned by post. An in-person visit is not required.

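### The follow-up depression adverse event is the absolute screening threshold, so an undivided count cannot separate new onset from symptoms already present at baseline

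*Combined protocol and SAP*

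**What the plan says.** Section 9.3.2.1 gives the BDI-FS two jobs.

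**At baseline** it is a screen. A total of 4 or more, or a response of 2 or 3 on item 7 (suicidal thoughts), calls for further evaluation. It does not exclude: after that evaluation, "individuals who have not passed the screen may be evaluated for eligibility for participation in the TRTT". Section 5.2.3.3 attaches a diagnosis to the same level: "The TRTT will define clinical depression as a score of 4 or greater on the Beck Depression Inventory-Fast Screen", or endorsement of item 7. On the consequence it says: "Any potential Study Participant who fulfills these criteria should be referred for appropriate counseling and may not be eligible for the TRTT". The exclusion in section 4.4.5 depends on function: "Is unable to participate fully in the trial or complete all followup visits because of an active or ongoing mental health condition". Table 4.1 lists no BDI-FS cut-off.

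**At follow-up** it is a safety measure. Repeating it "will permit Study Participants to be monitored for onset of serious depression as a possible consequence of treatment or other contributing factors". The definition comes next: "The TRTT will define the same threshold - a score of 4 or greater on the Beck Depression Inventory Fast Screen", or item 7 endorsed, is an adverse event, and the participant must be referred. No condition on the baseline score is given. Section 10.3 lists the instruments to be completed, "and the Beck Depression Inventory Fast Screen at each Follow-up Visit"; Table 10.2 puts the BDI-FS at 3, 6, 12 and 18 months and not later.

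Two related provisions matter. Section 2.2.3 plans an assessment of change from baseline in the BDI-FS, and section 9.1 treats the psychological measures as secondary outcomes whose change is monitored. Sections 2.4 and 3.3.3 send adverse effects to the DSMB and make it responsible for stopping rules.

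**The concern.** Onset means crossing the threshold from below. The definition asks only whether someone is above it. The two agree only if everyone enrolled starts below, and the plan does not require that. It also gives reason to expect some overlap: section 1.1.2 notes that "Significant correlations have been reported in the military population between tinnitus and depression and between tinnitus and sleep disturbances", and entry requires a Tinnitus Questionnaire score of at least 40.

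What is at stake is how a safety count reads. If depression events reach the DSMB or the final report as one total per arm, that total mixes depression that appeared on treatment with depression the participant brought in. Carry-over adds a similar background to each arm and pulls the ratio between arms towards one.

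**Working it through.** The plan gives no expected depression event rate and no baseline BDI-FS prevalence, so there is no figure to reproduce. The check is of the text first; illustrative arithmetic follows.

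**1. Can people who screen positive be randomized?** Yes. Sections 9.3.2.1 and 5.2.3.3 lead to evaluation and referral, and section 4.4.5 excludes only when the condition prevents participation or follow-up.

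**2. What the definition does with each path** (item 7 not endorsed):

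| Baseline | Follow-up | Adverse event? | Onset? |
|---|---|---|---|
| below 4 | 4 or more | yes | yes |
| 8 | 8 | yes | no |
| 8 | 5 | yes | no |
| 8 | below 4 | no | no |

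Improvement is counted only while the score stays at 4 or more, or item 7 is still endorsed.

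**3. How often?** There are four scheduled BDI-FS follow-ups, so one participant with stable symptoms can qualify four times. Section 9.3.2.1 does not say whether that is one event or four.

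**4. How many participants?** From section 2.3: 228 enrolled and 10% attrition, so 228 × 0.90 = 205.2 followed. Assumed, with no source in the documents: b, the share positive at baseline; s, the share of those still positive at a given visit; i, new onset among the rest. Baseline positives flagged at one visit = 205.2 × b × s.

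| b | s = 0.5 | s = 0.8 |
|---|---|---|
| 0% | 0 | 0 |
| 2% | 2.1 | 3.3 |
| 10% | 10.3 | 16.4 |
| 20% | 20.5 | 32.8 |
| 40% | 41.0 | 65.7 |

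Some of these would score higher than at baseline, so the figures are upper bounds for the group that is unchanged or lower.

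**5. When do they make up half of all those flagged?** Their share is b·s / (b·s + (1 − b)·i), which equals one half when b = i/(s + i).

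- i = 0.05: 0.05/0.55 = 9.1% (s = 0.5); 0.05/0.85 = 5.9% (s = 0.8)
- i = 0.10: 0.10/0.60 = 16.7% (s = 0.5); 0.10/0.90 = 11.1% (s = 0.8)

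**6. Effect on a comparison of arms.** Take b = 0.20 and s = 0.8 in both arms, with new onset of 5% in one and 15% in the other, a true ratio of 3.0. Under the absolute rule the arms show 0.20 × 0.8 + 0.80 × 0.05 = 0.20 and 0.20 × 0.8 + 0.80 × 0.15 = 0.28, a ratio of 1.4.

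**The case against.** The strongest reply is that section 9.3.2.1 describes an instrument, while the rules for grading, counting and reporting adverse events belong in Chapter 15, and their analysis in Chapter 23. Neither is in the part supplied. This stands: if Chapter 15 already classifies these events against baseline, only a cross-reference is needed.

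Second, change in the BDI-FS is already planned (sections 2.2.3 and 9.1). That stands in part. The data exist, so onset can be derived. A change-score analysis does not by itself separate onset from persistence, though, and does not alter what is recorded as an adverse event.

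Third, several filters limit entry of depressed people: professional evaluation, the functional exclusion, the audiologist's discretion (section 4.4.1) and the 12-month bar on tinnitus treatment, which includes psychological care (section 4.3). Randomization balances the remainder in expectation. This stands as a reason the number may be small, but none of these filters is a BDI-FS cut-off.

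Fourth, broad capture is the cautious choice. That stands for referral and for recording. Counting only onset, or only a set rise in score, would drop persistent suicidal thoughts, relapse after remission and a rise from 4 to 7 from adverse event reporting. A reader might infer that the definition should be narrowed in this way; it should not be.

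A reader might also infer that a harmful arm would look safer to the DSMB. Arithmetic allows it: with b = 0.20, 10% onset and 50% persistence give 0.10 + 0.08 = 18% flagged, while 5% onset and 80% persistence give 0.16 + 0.04 = 20%. But this needs one arm both to double onset and to relieve far more existing depression. With 76 × 0.90 = 68.4 per arm, it amounts to 12.3 against 13.7 participants, too small a gap to read as a difference.

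**Conclusion.** The mismatch in the text is real. The stated purpose is onset, the definition is an absolute level, and people already at that level can be enrolled. Followed as written, the rule labels unchanged or partly improved symptoms as adverse events, and an undivided count by arm cannot answer the onset question.

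The size is unknown. It is zero if no baseline-positive participants are enrolled; every rate used above is an assumption, and no power is claimed. A reader might go further and infer that the trial's safety monitoring or stopping decisions are compromised. The documents do not support that: the part supplied contains no between-arm test of these events, no stopping rule that uses the BDI-FS, and no statement that the DSMB receives a single undivided total.

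This is a minor improvement to classification and reporting. It rests on Chapter 15 not already providing it.

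**What to change.** Keep the absolute threshold as it is for referral and for recording adverse events, including any item 7 endorsement. Add to section 9.3.2.1, or to Chapter 15 with a cross-reference, that each event is classified by baseline status and change, taking the first class that applies:

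1. new onset: below threshold at baseline, or item 7 newly endorsed or increased;
2. recurrence after a visit below threshold;
3. at or above threshold at baseline, with a higher score now;
4. at or above threshold at baseline, unchanged or lower.

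Tabulate the four classes by arm for the DSMB and the final report, counting participants as well as visits. Use new onset among participants below threshold at baseline as the treatment-emergent measure. Persistent events stay in adverse event reporting. Do not add a fixed worsening margin, such as 4 points borrowed from the cut-off: the documents give no basis for one.

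The cost is one or two sentences and a small extra table. Baseline and follow-up BDI-FS scores are already collected, so no new data or visits are needed.

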### **9.3.2.2 State-Trait Anxiety Inventory**

The State-Trait Anxiety Inventory (Spielberger, Gorsuch, Lushene, Vagg and Jacobs, 1983) has been used extensively in research and clinical practice as a self-report measure of trait anxiety (or anxiety "proneness") and state anxiety (i.e., transitory anxiety experienced under specific conditions). The State-Trait Anxiety Inventory consists of 20 items for each subscale. The entire State-Trait Anxiety Inventory can be completed in approximately 10 minutes; a single subscale can be completed in about 6 minutes. It should be noted that the instrument is always referred to as the "Self-Evaluation Questionnaire" when speaking to respondents; the term anxiety is never used to describe the focus of the instrument. The State (i.e., how an individual feels at this moment) subscale's four-point response scale options are "Not At All, Somewhat, Moderately So, and Very Much So." The Trait (i.e., how one generally feels) subscale's response options include "Almost Never, Sometimes, Often, and Almost Always."

Prior to participation in the TRTT patients will complete both subscales of the State-Trait Anxiety Inventory ; only the State subscale, in which change is typically evidenced as conditions change, will be administered at the 6- and 18-month Follow-up Visits. Trait anxiety will be evaluated only to explore its possible role as a prognostic indicator.

